# 4.2 METHOD OF TREATMENT ASSIGNMENT

Randomization to the two treatment groups will be utilized. The study is not masked.

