# **Treatment Period**

# Baseline/Day 0/Month 0 (may occur at same time as screening visit)

The following information will be collected:

- Inclusion/exclusion
- Informed consent documentation
- Demographics
- Medical history and concurrent illnesses
- Concomitant medications
- AEs

The following procedures and assessments will be conducted:

- ETDRS visual acuity with manifest refraction
- Slit lamp examination
- Fundus examination
- Spectral Domain OCT evaluation
- Intravitreal injection of ranibizumab
- Pulse and blood pressure

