#### 4.8.3 Efficacy Analyses

#### a. Secondary Endpoints

- Mean change from baseline in best-corrected visual acuity by the number of letters read correctly at months 6 and 12.
- Mean absolute change from baseline central foveal thickness at months 6 and 12 as measured by SDOCT (defined as the average thickness within the central 1 mm subfield)
- Proportion of eyes that were anatomically "dry" by SDOCT at months 6 and 12.
- Proportion of eyes gaining greater than or equal to 15 letters of vision at months 6 and 12.
- Proportion of eyes losing greater than or equal to 15 letters of vision at months 6 and 12.
- Proportion eyes with 20/40 or better best-corrected visual acuity at months 6 and 12.
- Comparison of angiography leakage from baseline to months 3, 6, and 12.
- Comparison of peripheral nonperfusion from baseline to months 3, 6, and 12.
- Comparison of previous anatomic anti-VEGF response to month 3, month 6, and month 12 anatomic response.
- Comparison of previous functional anti-VEGF response to month 3, month 6 and month 12 functional response

٠

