REACT Study

Safety and Efficacy of Intravitreal Ranibizumab for Diabetic Macular Edema Previously Treated with Intravitreal Bevacizumab: A Randomized Dual-Arm Comparative Dosing Trial (Phase:1/2):

IND 120427

NCT01982435

Statistical Analysis Plan

11-07-2013

Measures for this study will be summarized using means, range and standard error of the means (SEM).

Two-sided paired t-tests and two-sided unpaired t-tests will respectively be conducted to analyze efficacy endpoints between study initiation to end, and between monthly and Treat and extend injection regimens. Patients who exit the study early can be accounted for by using a last observation carried forward approach. Chi-squared analysis will be used to assess significant differences in ophthalmic adverse event frequency. All analyses will be performed using GraphPad Prism 5 (GraphPad Software, La Jolla, California, USA) with a significance level of 0.05 being assumed for all tests

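### The between-regimen t-test on change in BCVA and central thickness leaves out the collected baselines; with 15 per arm, ANCOVA is the better pre-specified analysis (minor).

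*SAP*

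**What the plan says.** The SAP is a single section. Its only between-arm efficacy analysis is that "two-sided unpaired t-tests will respectively be conducted to analyze efficacy endpoints" over the course of the study "and between monthly and Treat and extend injection regimens". It names no covariate, regression or ANCOVA. For description it says "Measures for this study will be summarized using means, range and standard error of the means (SEM").

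Protocol 4.8.3 lists the two continuous endpoints at issue, "Mean change from baseline in best-corrected visual acuity by the number of letters read correctly at months 6 and 12" and "Mean absolute change from baseline central foveal thickness at months 6 and 12 as measured by SDOCT". It names no test or adjustment, so nothing there fills the gap. The SAP does not say whether the unpaired test is applied to change or to follow-up values. Read with the protocol's endpoint definitions, it is change.

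Both baselines are available. The Baseline/Day 0 schedule in protocol 4.5.1 includes "ETDRS visual acuity with manifest refraction" and "Spectral Domain OCT evaluation". On allocation, protocol 4.2 says "Randomization to the two treatment groups will be utilized" and adds only that the study is unmasked. Section 3.1 gives 15 patients per arm. Section 4.1.2 admits acuity from 20/25 to 20/320 and requires foveal fluid, but sets no thickness limit.

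**The concern.** A t-test on change assumes that a patient who starts one letter (or one micron) higher also ends exactly one higher, a slope of 1. If the true slope differs, part of any chance baseline difference between the arms passes into the estimated regimen difference. Nothing described in the protocol balances the arms on either measure, and 15 per arm is too few to rely on randomization alone to do so.

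Comparing the regimens is a stated aim (protocol section 2). There is no sample size calculation (4.8.1), so the useful product of this comparison is an estimate with its uncertainty. That estimate should not depend on which arm happened to start with better acuity or thinner maculas. From means and SEMs of change a reader can rebuild the unadjusted interval, but not a baseline-adjusted one. No primary safety conclusion is affected.

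**Working it through.** The plan states no SD, correlation, effect size or power, so there is no figure to reproduce.

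**Inputs**
- From the documents: 15 per arm (3.1); no stratification described (4.2); change-from-baseline endpoints (4.8.3); two-sided 0.05 (SAP).
- Assumed: correlation ρ between baseline and follow-up; k = follow-up SD / baseline SD; SD of BCVA change 8 to 12 letters.

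**1. Chance of imbalance.** The standard error of the baseline mean difference is √(2/15) = 0.365 SD. P(difference > 0.5 SD) = 2[1 − Φ(0.5/0.365)] = 0.171, for each baseline measure.

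**2. Shift in the unadjusted BCVA difference at an imbalance of exactly 0.5 SD.** Shift = |ρk − 1| × 0.5 × SD_base, where SD_base = SD_change/√(1 + k² − 2ρk).
- k = 1, ρ = 0.9, SD 8: SD_base = 8/√0.2 = 17.9; shift = 0.1 × 0.5 × 17.9 = 0.89 letters.
- k = 1, ρ = 0.5, SD 12: SD_base = 12; shift = 0.5 × 0.5 × 12 = 3.0 letters.
- k = 1.1 to 1.25, ρ = 0.8 to 0.9: from 0 (k = 1.25, ρ = 0.8, where ρk = 1) to 1.34 letters (k = 1.25, ρ = 0.9, SD 12).
- For scale, the unadjusted 95% CI half-width is 2.0484 × SD × √(2/15) = 5.98, 7.48 and 8.98 letters for SD 8, 10 and 12.

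**3. Precision.** Variance ratio, ANCOVA to change score = k²(1 − ρ²)/(1 + k² − 2ρk) = 1 − (ρk − 1)²/(1 + k² − 2ρk), which never exceeds 1. Allowing for the estimated slope and the lost degree of freedom, the average CI width ratio = √(variance ratio × 28/27) × 2.0518/2.0484.

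| k | ρ | Variance ratio | CI width ratio |
|---|---|---|---|
| 1 | 0.3 | 0.65 | 0.822 |
| 1 | 0.5 | 0.75 | 0.883 |
| 1 | 0.7 | 0.85 | 0.940 |
| 1 | 0.8 | 0.90 | 0.968 |
| 1 | 0.9 | 0.95 | 0.994 |
| 1.1 | 0.8 | 0.968 | 1.004 |
| 1.1 | 0.9 | 1.00 | 1.020 |
| 1.25 | 0.8 | 1.00 | 1.020 |
| 1.25 | 0.9 | 0.95 | 0.994 |

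The ceiling, at variance ratio 1, is 1.020. For BCVA (ρ 0.5 to 0.9) the interval runs from 12% narrower to 2% wider. For thickness (k = 1, ρ 0.3 to 0.7) it is 6% to 18% narrower. Simulation agrees with the BCVA width ratios to within 0.001.

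**4. Error rates by simulation** (100,000 trials per ρ, k = 1). Over all randomizations both methods reject a true null about 5% of the time. Among trials with an imbalance above 0.5 SD:

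| ρ | t-test on change | ANCOVA |
|---|---|---|
| 0.3 | 14.1% | 4.9% |
| 0.5 | 11.8% | 5.2% |
| 0.7 | 9.0% | 5.1% |
| 0.8 | 7.7% | 4.7% |

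**The case against.** The strongest reply is that this is a preference between two valid methods. The t-test on change is unbiased over randomizations and holds its 5% level. It already removes part of any imbalance, and no passage contradicts another on the point. All of that stands, and it is why the point concerns the choice of method and not an error.

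The benefit also rests on assumed inputs. At k = 1 and ρ 0.8 to 0.9 the BCVA interval narrows by only 0.6% to 3%, and with growing spread it can widen. Even a 3.0-letter shift lies inside the interval. Some of the assumed range fits the entry criteria poorly. At k = 1 and ρ = 0.9, SDs of change of 8 to 12 imply a baseline SD of 18 to 27 letters. Acuity spread uniformly over 20/25 to 20/320 (about 55 letters at 0.02 logMAR each) has an SD of only 55/√12 ≈ 16. Dropping those cases removes the smallest precision gains but also the smallest shifts at k = 1, so it does not favour either side.

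The 2% ceiling is an average over randomizations. With a 0.5 SD imbalance, the slope and degree-of-freedom cost is √[(2/15 + 0.25/28)/(2/15)] × 2.0518/2.0484 = 1.035, or about 3.5%; at 0.75 SD it is about 7.4%. At 0.5 SD and k = 1 the net effect is an interval 1.8% narrower at ρ = 0.8 and 0.8% wider at ρ = 0.9. In those cases the gain is the corrected estimate, with little or none in precision.

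Finally, these are secondary endpoints in a 30-patient pilot, and a reader shown Day 0 means would see an imbalance. Seeing it does not supply the adjusted estimate, and a covariate added after the imbalance is known invites a charge of selective analysis.

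**Conclusion.** The concern holds and is minor. For two continuous endpoints whose baselines are collected, the SAP names a between-arm test that ignores those baselines except by subtraction. ANCOVA is a specific, better choice. The case rests mainly on protection from chance imbalance: a 17% chance per measure of more than 0.5 SD, with a BCVA shift at 0.5 SD of 0.9 to 3.0 letters at k = 1, or 0 to 1.3 letters at k 1.1 to 1.25 with ρ 0.8 to 0.9. Precision usually improves, by an amount the documents cannot settle, and the worst average loss is about 2% in interval width. Only the 17% follows from the documents' sample size alone (with a normal approximation and simple randomization); the rest depends on the assumed ρ, k and SD of change. The primary safety analysis is untouched.

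**What to change.** For BCVA and central foveal thickness at months 6 and 12, replace the between-regimen unpaired t-test with an ANCOVA of the follow-up value on arm and the Day 0 value of the same measure. Using change as the outcome gives the same arm difference. Report the adjusted difference with its 95% CI, and fix this before any comparison by arm is seen.

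Use the same patients and missing-data rule as the test it replaces. That rule needs settling separately, because protocol 4.8.4 specifies available cases without imputation while the SAP permits last observation carried forward.

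The cost is two SAP sentences and one residual degree of freedom (28 to 27), with no new data or visits. If the software package named in the SAP does not fit the model, another must be named.

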# 3. STUDY DESIGN

# 3.1 DESCRIPTION OF THE STUDY

This is an open-label, Phase I/II study of intravitreally administered 0.3mg ranibizumab in subjects with DME previously treated with intravitreal bevacizumab with a randomized comparative dosing strategy (monthly vs "treat-and-extend"). Thirty patients total will be enrolled in the study, 15 in each group. This study will have a 1-year treatment period. The recruitment period will occur over 1 year with a total potential study duration of 2 years. Interim analysis performed at 6 months and final analysis at 1 year.

Group 1 (monthly group) n=15

Consented, enrolled subjects will receive multiple open-label intravitreal injections of 0.3 mg ranibizumab administered every 30 days (+/- 7 days from the last treatment) for 12 months in the monthly group.

Group 2 ("treat-and-extend" group) n=15

 In the "treat-and-extend" group, eyes will be treated with 3 loading doses at 30-day intervals (+/- 7 days from the last treatment). After the third loading dose, the follow-up interval is determined with an OCT-based protocol.

Angiography assessment:

Both qualititative and quantitative assessment of angiographic features will be performed on obtained angiograms. This will include evaluation of leakage, microaneurysms and ischemia. This is detailed in Appendix D. Addendum for

Prior anti-VEGF response assessment:

Utilizing available clinical and imaging data contained in the medical record, assessment of functional (visual acuity) and anatomic (OCT) responses will be assessed. This information would be assessed in detail following review of this data for appropriate inclusion/exclusion parameters for the study. This is detailed in Appendix E.

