# 3.3 OUTCOME MEASURES

#### 3.3.1 Primary Outcome Measures

The primary outcome measures for safety and tolerability are the following:

- Incidence and severity of ocular adverse events, as identified by eye examination (including visual acuity testing)
- Incidence and severity of other non-ocular adverse events, as identified by physical examination, subject reporting, and changes in vital signs

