#### 4.8.5 Interim Analyses

An interim analysis is planned at 6 months. Reports of adverse events from this study may be reviewed and summarized periodically while the study is ongoing to ensure the safety of subjects.

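### The SAP tests unranked secondary efficacy endpoints at an unadjusted 0.05 and does not call them exploratory, so a chance result could be reported as significant

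*SAP*

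**What the plan says.** The SAP sets the tests and their level in one short paragraph:

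- On efficacy: "Two-sided paired t-tests and two-sided unpaired t-tests will respectively be conducted to analyze efficacy endpoints". The paired tests compare the start of the study with its end. The unpaired tests compare the monthly and treat-and-extend regimens.
- On safety: "Chi-squared analysis will be used to assess significant differences in ophthalmic adverse event frequency".
- On the level: "with a significance level of 0.05 being assumed for all tests".

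The protocol supplies the endpoints and the timing of analyses:

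- Section 3.3.1 makes the primary outcomes safety ones: "The primary outcome measures for safety and tolerability are the following", followed by ocular and non-ocular adverse events. Section 4.8.2 repeats this. The opening of section 2 does call effectiveness the primary objective, but sections 2.1, 3.3.1 and 4.8.2 all designate safety.
- Section 4.8.3 lists ten efficacy endpoints, all as secondary. Six are read at two visits, for example "Mean change from baseline in best-corrected visual acuity by the number of letters read correctly at months 6 and 12". Four are read at three visits, for example "Comparison of angiography leakage from baseline to months 3, 6, and 12".
- Section 3.1 gives the timing: "Interim analysis performed at 6 months and final analysis at 1 year". Section 4.8.5 says "An interim analysis is planned at 6 months", and then mentions periodic review of adverse events.
- Section 4.8.1 calls the study a pilot and gives no sample size calculation.

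Neither document ranks the efficacy endpoints, adjusts for their number, labels the p-values as descriptive or says what the interim analysis covers.

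**The concern.** A 0.05 level limits error for one test. Applied to a list of endpoints and visits with no order of importance, it gives no way to tell a planned finding from the best of many. Any result with p<0.05 may be called significant under the SAP as written.

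What is at stake is the reading of the secondary results. Section 4.8.1 looks ahead to a possible phase II/III trial, and a chance difference between regimens could influence how that trial is designed. With 15 patients per arm, such a difference would also look large. An unpaired t-test with 28 degrees of freedom reaches p<0.05 only when the observed difference is at least 2.048 × √(2/15) = 0.75 standard deviations.

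**Working it through.** The documents state no overall error rate or power, so the only planned figure is the per-test level of 0.05. The rest is a count of tests.

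**Inputs**

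- Level per test: 0.05, two-sided (SAP).
- Six endpoints at months 6 and 12 (protocol 4.8.3): change in visual acuity, change in foveal thickness, dry on OCT, gain of 15 letters or more, loss of 15 letters or more, and 20/40 or better. 6 × 2 = 12.
- Two angiographic endpoints at months 3, 6 and 12: leakage and nonperfusion. 2 × 3 = 6.
- Two prior-response endpoints at months 3, 6 and 12, anatomic and functional. 2 × 3 = 6. Each compares a patient's earlier anti-VEGF response with the response on study, so these are within-patient items.
- Allocation: 15 per arm (protocol 3.1).

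**Between-arm tests**

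- All visits, without the prior-response items: 12 + 6 = 18.
- Final visit only, one test for each of the ten endpoints: 10. Leaving out the two prior-response items here as well gives 8.

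**Formulas, if every tested effect is null**

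- Expected false positives = m × 0.05. This holds whatever the correlation.
- Chance of at least one = 1 − 0.95^m under independence. For correlated tests it was simulated with equally correlated normal test statistics. The correlations are assumptions, since the documents give none.

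| Tests (m) | Expected false positives | At least one, independent | Correlation 0.3 | Correlation 0.5 |
|---|---|---|---|---|
| 8 | 0.4 | 34% | 30% | 25% |
| 10 | 0.5 | 40% | 35% | 29% |
| 18 | 0.9 | 60% | 51% | 40% |

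For example, 18 × 0.05 = 0.9 and 1 − 0.95^18 = 0.60.

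**Binary endpoints.** Four of the endpoints are proportions, which makes 8 of the 18 tests. Exact enumeration at 15 per arm shows that the real size of the nominal 0.05 test is 0.5% at a true event rate of 5%, 2.5% at 10% and 5.0% at 20%. Suppose, as an assumption, that loss of 15 letters occurs in 5% of eyes and gain of 15 letters in 10%, at both visits. The expected count then falls from 0.9 to 14 × 0.05 + 2 × 0.005 + 2 × 0.025 = 0.76.

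**Paired tests.** The SAP wording implies one start-to-end contrast per endpoint. Gain and loss of 15 letters are already changes from baseline and have no baseline value to pair. Other contrasts are unlikely to be null: every patient receives active drug, and fluid at the foveal centre is an entry criterion (protocol 4.1.2), so no eye should be dry at baseline. A real change is not a false positive, so paired tests add to the count only where there is truly no change.

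**Not counted.** The chi-squared comparison of adverse events adds at least one test, but the number of event categories is not given. The number of injections (protocol 2.2) differs between regimens by design.

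**The case against.** The strongest reply is that little depends on these tests. The primary outcome is designated and is safety. Every efficacy endpoint is secondary, in a 30-patient pilot with no sample size calculation. The reasons for ending the study in section 4.7 include no efficacy result, and section 4.8.1 leaves the statistical analysis of a later trial to be determined then. All of this stands, and it is why the point is minor. It does not remove the point, because the SAP still commits to significance testing and nowhere says that the results are exploratory.

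The size can also be overstated. A reader might infer any of the following, and the documents do not support them:

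- *48 tests, with 2.4 false positives expected and a 91% chance of at least one.* This assumes a paired test at every visit. The SAP describes paired tests only from the start to the end of the study, and several of them are unlikely to be null.
- *24 between-arm tests, with 1.2 expected and a 71% chance.* Six of the 24 endpoint-by-visit results are the within-patient prior-response items.
- *Interim efficacy tests by arm at 0.05, raising the error for one endpoint to 8.3%.* No section says that efficacy is compared by arm at the interim, and the SAP does not mention an interim. The 8.3% assumes two looks at one endpoint with equally spaced information. Months 6 and 12 are listed as separate results, so the month-6 tests are already in the count of 18.
- *Interim results biasing later treatment or assessment.* The study is unmasked (section 4.2), and staff already see each patient's regimen, acuity and OCT at treatment visits. The documents do not show that an interim summary would add materially to that.

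Independence is also generous to the concern. Four endpoints derive from the same letter score, and the visits repeat on the same eyes.

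**Conclusion.** The point holds at modest size. The SAP applies an unadjusted 0.05 to all tests, and the efficacy endpoints are secondary, unranked and repeated over visits. If all between-arm effects are null, 0.5 to 0.9 false positives are expected. The chance of at least one is 40% to 60% under independence, and about 29% to 51% at correlations of 0.3 to 0.5. If the prior-response items are also excluded at the final visit, the lower end becomes 0.4 expected and 34% under independence.

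These figures rest on a count from section 4.8.3, because the SAP does not list its tests. They do not show that a spurious finding is certain, or even more likely than not in every case. They show that the stated rule cannot separate such a finding from a planned result. As for the interim, its content is simply undefined. Severity is minor, because the primary outcome is safety and no decision rule depends on these p-values.

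**What to change.** Change the SAP wording in three places:

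1. Report all efficacy comparisons, between arms and within patients, as estimates with 95% confidence intervals. Label them exploratory, and state that no claim of significance will be made from p<0.05 alone.
2. If the sponsor wants one confirmatory-style efficacy test, name a single endpoint and visit in advance. Between-arm change in best-corrected visual acuity at Month 12 is an example, since that endpoint is listed first. One such test carries a 5% error rate. No splitting of the 0.05 level is then needed.
3. State what the 6-month interim contains: either a safety summary, or a summary in which any month-6 efficacy result is descriptive and carries no claim of significance.

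The cost is SAP text only, with no added patients, visits or measurements. In return, secondary p-values can no longer be described as significant.
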